6.2 DURATION OF STUDY PARTICIPATION

6.2.1 Duration of study participation for each patient

Main open-label treatment phase:

For Cohorts 1 to 3, a study duration of approximately 16-23 weeks (screening/run in period: up to 6 [+1] weeks, main open-label treatment period: 8 weeks, follow-up period: 6-8 weeks)

For Cohort 4, a study duration of approximately 14-19 weeks (screening period: up to 6 [+1] weeks, open-label dose-finding treatment period: 12 weeks).

Open-label extension phase:

Patients who enroll in the open-label extension treatment period will continue alirocumab administration until at least 10 weeks before the initiation of the pediatric Phase 3 study in the site where the patient is potentially participating. Therefore, patients who consent to participate in the pediatric phase 3 study could have their last alirocumab injection in the OLE period up to December 2018, depending on timing of site initiation for the phase 3 study planned to be done no later than December 2018. All other patients, enrolled in the OLE period, who decline the participation in the phase 3 study, will have their last alirocumab injection on December 2018. This corresponds to a maximum of approximately 24 months for the first patients enrolled in Cohorts 1 to 3. For Cohort 4, this corresponds to a maximum of approximately 7 months for the first patients enrolled.

For both phases, patients who experience an ongoing Serious Adverse Event (SAE) or an Adverse Event of Special Interest (AESI), at the pre-specified study end-date, should be followed until resolution, stabilization, or death and related data will be collected.

End of study per patient:

If patient does not participate to the open label extension period, then the end of the study is the last on site visit as scheduled by protocol (ie, visit Week 14 or Week 12 (Cohorts 3 & 4, respectively) or Week 16 (Cohorts 1 & 2) or the resolution/stabilization of all SAEs, and AESI, whatever comes last.

If patient participates in the open label extension period, then the end of the study is the last on site visit as scheduled by protocol (ie, visits will continue until visit end of OLE at least 2 or 4 weeks after last alirocumab injection (with a follow-up phone call at least 10 weeks after the last alirocumab administration) before the initiation of the pediatric Phase 3 study in the site where the

patient is potentially participating or December 2018, at the latest, or the resolution/stabilization of all SAEs, and AESI, whatever comes last.

A follow-up phone contact will take place at least 10 weeks after the last IMP of each cohort, including Cohort 4.

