1.2 GRAPHICAL STUDY DESIGN (OPTIONAL EXTENSION PHASE)

1.2.1 COHORTS 1 TO 3

1.2.2 COHORT 4

OPEN-LABEL EXTENSION (OLE) PERIOD

- * All patients enrolled in Cohort 4 who successfully complete the main phase will be offered entry into the extension phase at Week 12 or directly switch to the phase 3 study (EFC14643).
- ** Visits will continue until at least 6 weeks (corresponding to the wash out period of 10 weeks after the last alirocumab injection) before the initiation of the pediatric Phase 3 study in which the site where the patient is potentially participating where the latest end date for Cohort 4 will be December 2018.
- *** A follow-up phone call will take place at least 10 weeks after the last IMP for all cohorts, except those patients who refuse phase 3.
- **** The Q4W dose for Cohort 4 administered during the open label-dose finding treatment period of the main phase will initially be continued in the extension phase.

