For Cohorts 1- 3, the initial dose of alirocumab that will be administered during the extension phase, will be the continuation of same doses/regimens administered during the main phase up to the time when the final optimal doses for the Phase 3 study are selected and prefilled syringes

available. Then these final optimal doses will be administered to all patients during the extension phase, based on their body weight at the time of dose change.

For Cohort 4, if patients enter the OLE phase, patients will continue on their doses from the main phase.

At the end of each study phase, patients are to be followed 10 weeks after last alirocumab injection on site (for main phase, only for Cohorts 1-3 as this follow up period doesn't apply for Cohort 4) or by phone (for extension phase, for all cohorts). Patients with any adverse event (AE) should be followed until resolution, stabilization, or death, as specified in the protocol.

Approximately 40 patients (10 patients per cohort) were to be enrolled from approximately 28 sites.

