2.1.4 Safety endpoints

The safety analyses will be based on the reported adverse events (AEs) and other safety information, such as clinical laboratory data, vital signs, and tanner stage assessment.

Observation period

The period of safety observation starts from the time when the patient gives informed consent and is divided into the following periods:

- The PRE-TREATMENT period: defined as the time from the signed informed consent up to the first dose of IMP injection in the study;
- The OLDFI treatment-emergent adverse event (TEAE) period: defined as the time from the first OLDFI IMP injection up to the day of last OLDFI IMP injection + 70 days (10 weeks) as residual effect of alirocumab is expected until 10 weeks after discontinuation. For patients entering in the OLE, the OLDFI TEAE period will be truncated at the day before the first OLE IMP injection in the extension period;

The OLDFI TEAE period will include:

- The OLDFI TREATMENT period: defined as the time from the first OLDFI IMP injection up to the day of last OLDFI IMP injection + 21 days (for Cohorts 1 & 2) or + 35 days (for Cohort 3 & 4) . For patients entering in the OLE, the OLDFI treatment period will truncated at the day before the first OLE IMP injection in the extension period
- The OLDFI POST-TREATMENT period defined as the time starting the day after the end of OLDFI TEAE period. For patients entering in the OLE, the OLDFI POST-TREATMENT period will be truncated at the day before the first OLE IMP injection in the extension period;
- The OLDFI/OLE combined TEAE period: defined as the time from the first OLDFI IMP injection up to the day of last OLE IMP injection (or to last OLDFI IMP injection for patients not entering into the extension phase) + 70 days ;

The OLDFI/OLE combined TEAE period will include:

- The OLDFI/OLE combined TREATMENT period defined as the time from the first OLDFI IMP injection up to the day of last OLE IMP injection (or to last OLDFI IMP injection for patients not entering into the extension phase) + 21 days (for Cohorts 1 to 2) or + 35 days (for Cohorts 3 & 4). For patients from Cohort 3 who switched to selected Phase 3 doses, the OLDFI/OLE combined TREATMENT period is defined as

the time from the first OLDFI IMP injection up to the day of last OLE IMP injection
+ 21 days.

- The OLDFI/OLE combined POST-TREATMENT period defined as the time starting the day after the end of the OLDFI/OLE combined TEAE period.

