2.1.4.1 Adverse events variables

Adverse events (including serious adverse events (SAEs) and adverse events of special interest (AESIs)) are recorded from the time of signed informed consent until the end of study. All AEs diagnosed by the Investigator will be reported and described.

All AEs will be coded to a “lowest level term (LLT)”, “preferred term (PT)”, “high level term (HLT)”, “high level group term (HLGT)” and associated primary “system organ class (SOC)” using the version of MedDRA currently in effect at Sanofi at the time of database lock.

Adverse event observation period

- Pre-treatment AEs are AEs that developed or worsened or became serious during the pre-treatment period.
- OLDFI treatment-emergent adverse events are AEs that developed or worsened or became serious during the OLDFI TEAE period.
- OLDFI post-treatment AEs are AEs that developed or worsened or became serious during the OLDFI post-treatment period.
- OLDFI/OLE combined treatment-emergent adverse events are AEs developed or worsened or became serious during the OLDFI/OLE combined TEAE period.
- OLDFI/OLE combined post-treatment AEs are AEs that developed or worsened or became serious during the OLDFI/OLE combined post-treatment period.

Groupings of Adverse events

Grouping of Adverse events include the following:

- Local injection site reactions (AESIs or not), selected using e-CRF specific tick box on the adverse event page

- Allergic events
 - General allergic events (AESIs or not), selected using SMQ “hypersensitivity” (broad and narrow) excluding the following preferred terms linked to local injection site reactions (“infusion site dermatitis”, “infusion site hypersensitivity”, “infusion site rash”, “infusion site urticaria”, “injection site dermatitis”, “injection site hypersensitivity”, “injection site rash”, “injection site urticaria”, and “injection site vasculitis”)

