If applicable, similar summaries of TEAEs as those described above will be also provided on the safety subgroup population of patients with two consecutive results of calculated LDL-C <50 mg/dL (respectively calculated LDL-C <25 mg/dL) (as defined in [Section 2.1.4.7](#)). Only TEAE for which it will be confirmed or unclear that they occurred, worsened or became serious the day or after the first level of LDL-C <50 mg/dL (or LDL-C <25 mg/dL) will be considered. In case very few cases are observed, individual data listings of TEAEs will be provided on this subgroup of patients instead.

In addition, for the OLDFI/OLE combined period, the following summary tables will be provided:

- The event rate per patient year (the number of patients with an event in question divided by total patient-years) will be provided for all TEAEs by SOC and PT. For a patient with event, patient year is censored at time of first event; for patient without event, it corresponds to length of OLDFI/OLE combined TEAE period
- Kaplan-Meier curves will be provided, when appropriate, for time from first dose of OLDFI IMP to the first occurrence of selected TEAEs. Patients without any event will be censored at the end of the OLDFI/OLE combined TEAE period.

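### Cohort 4 completers who do not enter the extension: the SAP counts at-risk time to Week 18 with no cap at last contact, while the last scheduled visit is at Week 12 and the Week 18 phone call is not clearly theirs

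*Protocol*

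**What the plan says.** **Dosing and exits.** Cohort 4 is dosed at Weeks 0, 4 and 8 (Protocol 6.1). After Week 12 a completer may enter the extension, decline it, or go directly into Phase 3 (Protocol synopsis, SAP 1.1).

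**End of study.** For patients outside the extension, Protocol 6.2.1 gives "the last on site visit as scheduled by protocol (ie, visit Week 14 or Week 12 (Cohorts 3 & 4, respectively"), extended if an SAE or AESI is unresolved. Flowchart 1.3.2 stops at Week 12. Protocol 10.1.3 makes the follow-up period mandatory for Cohorts 1-3 only. SAP 1.1 says patients are "to be followed 10 weeks after last alirocumab injection on site (for main phase, only for Cohorts 1-3"), and ties phone follow-up to the extension phase. AEs are "recorded from the time of signed informed consent until the end of study" (SAP 2.1.4.1).

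**The phone call.** Section 6.2.1 closes with: "A follow-up phone contact will take place at least 10 weeks after the last IMP of each cohort, including Cohort 4". The procedures for that call appear only under the extension (flowchart 1.4.2, Protocol 10.1.4.7).

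**At-risk time.** SAP 2.1.4 runs the combined TEAE period to the last extension injection, "or to last OLDFI IMP injection for patients not entering into the extension phase) + 70 days". In SAP 2.4.5.1 this length enters the event rate per patient-year, where "for patient without event, it corresponds to length of OLDFI/OLE combined TEAE period", and the Kaplan-Meier curves: "Patients without any event will be censored at the end of the OLDFI/OLE combined TEAE period".

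**Follow-up flag.** For the main phase, SAP 2.2 counts follow-up as sufficient only with an on-site post-treatment visit more than 9 weeks after the last injection. A phone call counts only for the extension period.

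**The concern.** In Cohorts 1-3 the 70-day window and the visit schedule agree, because the final follow-up visit falls 10 weeks after the last dose. Cohort 4 dropped that visit but kept the window. Whether anyone contacts a Cohort 4 completer between Weeks 12 and 18 depends on one sentence in 6.2.1 that the flowchart, the visit procedures and SAP 1.1 do not carry through.

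If a site follows the flowchart, those weeks enter the denominator as event-free time without anyone having asked about events. Rates per patient-year are then too low, and the Kaplan-Meier curves hold patients at risk past their last contact. The cohort concerned has the highest Q4W doses in the study, and Protocol 9.2.3.1 says residual drug effect is possible for 10 weeks.

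If the site does call, SAP 2.2 does not recognise the call, and the disposition table reports these patients as insufficiently followed.

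**Working it through.** **1. Reproduce the plan's stated durations (Protocol 6.2.1).** Screening takes 2 weeks (shortest, synopsis and 10.1.1) to 7 weeks (6 + 1).
- Cohorts 1-3: 2 + 8 + 6 = 16 and 7 + 8 + 8 = 23 weeks; stated 16-23.
- Cohort 4: 2 + 12 = 14 and 7 + 12 = 19 weeks; stated 14-19. The Cohort 4 figure leaves no room for contact after Week 12.
- Final follow-up visits: Cohorts 1 and 2, Week 6 + 10 = Week 16; Cohort 3, Week 4 + 10 = Week 14. Both match the 70-day window.

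**2. Window against schedule, Cohort 4 completer outside the extension.**
- Last dose: Day 57 (Week 8). TEAE end: 57 + 70 = Day 127 (Week 18). Length: 126 days = 0.345 patient-years.
- Last scheduled visit: Day 85 (Week 12). Length: 84 days = 0.230 patient-years.
- Gap: 126 - 84 = 42 days, one third of the window, or 0.115 patient-years per event-free patient.
- With visit windows (Week 8 ±3 days, Week 12 ±7 days), the gap is 32 to 52 days.

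**3. Effect on these patients' rate if no call is made.** Assume a constant hazard and no event captured after Week 12. The SAP rate is then 0.67 to 0.77 of the true rate, for true rates of 0.1 to 4 per patient-year.

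**4. Effect on Cohort 4 as a whole.** The number k of 10 patients not entering the extension is not stated, so it is an assumption. Let an extension entrant contribute L days, also assumed: from 154 (one extension dose at Week 12, 84 + 70) to 283 (about 7 months of dosing, 213 + 70). Taking all patients as event-free:

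excess = 42k / [84k + L(10 - k)]

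| k | L = 154 | L = 283 |
|---|---|---|
| 0 | 0% | 0% |
| 2 | 84/1400 = 6.0% | 84/2432 = 3.5% |
| 5 | 210/1190 = 17.6% | 210/1835 = 11.4% |
| 10 | 420/840 = 50% | 50% |

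**5. SAP 2.2 flag.** The latest Week 12 visit is 28 + 3 + 7 = 38 days after the Week 8 dose, against more than 63 days required. No such completer can pass on scheduled visits, and a Week 18 phone call does not count for the main phase.

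**6. Data cut-off.** The second-step analysis (SAP 3) cuts data at Cohort 4's last main-phase visit, so Week 18 can fall after the cut-off for late enrolees. The SAP 3 rules that end periods at the cut-off are written for the first analysis and for ongoing patients. They do not clearly shorten a completer's time at risk.

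**The case against.** The strongest reply is that the texts can be reconciled. Section 6.2.1 defines the end by the last on-site visit, and a phone call is not an on-site visit. The extension paragraph has the same form: an on-site end plus a later call. The closing line is not limited to extension patients. Protocol 9.2.3.1 also refers to 6.2.2, where the trial ends with the last visit or contact. On that reading the Week 18 call is required and the person-time is observed. This is a fair reading, so the documents do not establish that six weeks go unobserved, only that sites are not clearly told to make the call. It does not supply a cap for a call that is missed or falls after the cut-off, and it does not repair SAP 2.2.

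A reader might take the footnote in 1.2.2, which has the call "at least 10 weeks after the last IMP for all cohorts, except those patients who refuse phase 3", as a further contradiction. It belongs to the extension diagram, so it is weak evidence about patients who never enter the extension.

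Three further replies limit the point:
- Early discontinuers are to be followed for at least 10 weeks (Protocol 10.3.4) and can pass SAP 2.2. Only completers are concerned.
- Unresolved SAEs and AESIs are followed, and related SAEs learned of later are reportable (10.4.4). What could be missed is mainly new non-serious AEs.
- The main AE tables are n (%), without person-time. With about 10 patients, an exact 95% Poisson interval for 5 events runs from 1.6 to 11.7, far wider than a shift of a few percent.

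Dropping the follow-up period was a stated choice (Protocol 4), and the doses were endorsed by the DMC and Steering Committee. That supports the design, but not counting time that may not be observed.

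**Conclusion.** The point holds for Cohort 4 completers who do not enter the extension. As written, SAP 2.1.4 and 2.4.5.1 give each event-free one 126 days at risk whatever the last contact, and the schedule guarantees observation for 84. If the Week 18 call is not made, the unobserved share is one third at nominal visit days. If it is made, the rate is sound, but SAP 2.2 flags every such completer by construction. Either way a correction is needed.

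The cohort-level size rests on the unstated number not entering the extension: none if 0, about 3.5-6% excess patient-years if 2 of 10. A reader might infer that Cohort 4 rates are understated by a third. That requires all ten patients to stay out of the extension and no call to be made, and the documents support neither. The effect is confined to supplementary, descriptive person-time rates, Kaplan-Meier curves for selected events and one disposition table. The Week 8 LDL-C endpoint is untouched.

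**What to change.** 1. **SAP 2.1.4 and 2.4.5.1:** end at-risk and censoring time at the earliest of last injection + 70 days, last AE contact, and data cut-off.
2. **Protocol 6.2.1, flowchart 1.3.2, Protocol 10.1.4.7 and SAP 1.1:** state that the 10-week phone contact already named in 6.2.1 applies to Cohort 4 completers who do not enter the extension, covering AEs and concomitant medication.
3. **SAP 2.2:** accept that phone contact as sufficient follow-up for Cohort 4 in the main phase.

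The cost is at most about 10 phone calls, plus short edits to four SAP sections and three protocol places. It adds no blood draw and no site visit. The first change is worth making even if the calls are already intended, since it also covers a missed call.

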6.2.2 Determination of end of clinical trial (all patients)

The end of the clinical trial is defined as being the last visit/contact of the patients at the study level.

6.3 INTERIM ANALYSIS

No formal interim analysis is planned. However, analyses will be conducted at the end of the main phase to select the dose that will be used in the Phase 3 study.

6.4 STUDY COMMITTEES

Steering Committee:

The Steering Committee is composed of university-based physicians (experts in pediatric lipids field, and/or pediatric cardiology) with clinical and methodological expertise, working in collaboration with the Sponsor.

The Steering Committee will provide scientific and strategic direction for the trial and will have overall responsibility for its execution. The Steering Committee will provide guidance on producing and conducting a scientifically sound design and ensuring accurate reporting of the study. The Steering Committee will address and resolve scientific issues encountered during the study. The Steering Committee will also review the recommendations from the DMC throughout the study.

Among its responsibilities, the Steering Committee will review data during the conduct of the study. The Steering Committee will also review the recommendations from the Data Monitoring Committee throughout the study. The Steering Committee members and Sponsor will participate in regular meetings. Detailed activities and responsibilities of the Steering Committee are described in the Steering Committee charter.

Data Monitoring Committee (DMC):

The DMC is composed of external, independent expert physicians with experience in pediatric lipids field and/or pediatric cardiology. The independent DMC will monitor periodically patient safety by conducting reviews of accumulated safety data, including Cohort 4. The DMC will provide the Sponsor and the Steering Committee with appropriate recommendations on the conduct of the clinical trial to ensure the protection and safety of the patients enrolled in the study. In addition, the DMC will also institute any measures that may be required for ensuring the integrity of the study results during the study execution. The DMC will review data on a regular basis during the dose finding treatment period. The DMC is tasked to provide recommendations periodically and on dose escalation decision from Cohort 1 to Cohorts 2, 3.

All activities and responsibilities of the DMC are described in the DMC charter.

7 SELECTION OF PATIENTS

7.1 INCLUSION CRITERIA

Patients meeting all of the following inclusion criteria will be considered for enrollment into the study:

- I 01. Children and adolescent male and female patients aged 8**** to 17 years at the time of signed informed consent.
For Russia only:
Male and female patients aged ≥ 12 and ≤ 17 years at the time of signed informed consent
- I 02. Patients with diagnosis of heterozygous familial hypercholesterolemia (heFH) through genotyping or clinical critiera.*
- I 03. Patients treated with optimal dose of statin** \pm other LMT(s) or non-statin LMT(s) if statin intolerant*** at stable dose for at least 4 weeks.
- I 04. Patients with calculated LDL-C greater than or equal to 130 mg/dL (≥ 3.37 mmol/L) obtained during the screening period after the patient has been on stable LMT (ie, stable optimal dose of statin \pm other stable LMTs or stable non-statin LMTs in statin intolerant patients) treatment for at least 4 weeks.
- I 05. Patients with body weight greater than or equal to 25 kg.
- I 06. Patients aged of 8 to 9 years to be at Tanner stage 1 and patients aged of 10 to 17 years to be at least at Tanner stage 2 in their development.
- I 07. A signed informed consent indicating parental permission with or without patient assent, depending on capacity for understanding based on developmental maturity. In cases involving emancipated or mature minors with adequate decision-making capacity, or when otherwise permitted by law, a signed informed consent directly from patients.

* Diagnosis of heFH must be made either by previous genotyping, current genotyping, or by clinical criteria according to Simon Broome criteria. Previous genotyping refers to documented results that are available from prior genotyping testing supporting a diagnosis of heFH. Current centralized genotyping refers to patients consenting to undergo mandatory genotyping during the screening period with results supporting a diagnosis of heFH. The clinical diagnosis should be based on the Simon Broome criteria for possible or definite FH. (see [Appendix F](#)). Once eligibility is confirmed based on prior genetic testing or Simon Broome criteria, results of elective genetic testing will not impact patient's eligibility.

** The optimal dose of statin is defined as the stable daily dose prescribed based on regional practice or local guidelines or is the stable daily dose that is maximally tolerated due to adverse effects on higher doses. For patients not receiving the maximally tolerated dose of statin, statin intensification should be carefully considered prior to inclusion in this study in order to ensure that the addition of a non-statin LDL-C lowering therapy (ie, alirocumab) would be the next appropriate step in the management of the patient's hypercholesterolemia. The highest dose of statin should not exceed the maximum labeled dose of statin for pediatric patients as per the local prescribing information.

- *** Statin intolerant patient is defined as the inability to tolerate at least 2 statins: one statin at the lowest daily starting dose, AND another statin at any dose, due to skeletal muscle-related symptoms, other than those due to strain or trauma, such as pain, aches, weakness, or cramping, that began or increased during statin therapy and stopped when statin therapy was discontinued. Patients not receiving a daily regimen of a statin (eg, 1 to 3 times weekly) are also considered as not able to tolerate a daily dose.
- **** Patients age of 8 to less than 10 years have had other available interventions to lower calculated LDL-C but these have been insufficient.

